11.2 Final Study Visit

The subject's participation in this study is completed after 21-42 -days of follow-up or when the subject is discharged from the facility. At the final visit the following assessments will be completed:

- Medications
 - Review and record changes to current medications.
- Adverse Events
 - Assess and record adverse events. Immediately report any Serious Adverse Event. (Refer to Adverse Event CRF instructions).
- Perform Skin Cleansing and record pain score before and after cleansing
- Conduct Skin Assessment
- Take Photographs
- Administer Quality of Life questionnaire
- Healthcare Worker Ease of Use Survey
 - Complete end of study product Ease of Use survey
- Documentation
 - Complete and check all documentation.

Page 27 of 54 Status: Release Version: 7 Issue Date: 8/31/2016 12:19:02 PM

Page 28 of 54 Status: Release Version: 7 Issue Date: 8/31/2016 12:19:02 PM

Schedule of Events

Assessment	Screening/ Enrollment	D1 /23	D2 /24	D3 /25	D4 /26	D5 /27	D6 /28	D7 /29	D8 /30	D9 /31	D10 /32	D11 /33	D12 /34	D13 /35	D14 /36	D15 /37	D18 /38	D17 /39	D18 /40	D19 /41	D20 /42	D21 /43	End of Study/ D22/D44
Informed Consent	Х																						
Inclusion/Exclusion	Х																						
Urine Pregnancy Test	X																						
Demographics	X																						
IAD History & Current Product Use	х																						
Medications	Х	Х																					Х
Pressure Sore Risk Assessment	Х																						
Quality of Life questionnaire	x																						X
Skin Cleansing	X	Х	Х	Х	Х	Х	Х	Х	Х	Х	X	Х	Х	Х	Х	Х	Х	Х	Х	Х	Х	Х	Х
*Skin Cleansing – Timing & Product Use	х			X																			
Skin Assessment / IAD scoring	X	X		X		X			X		X		Х			X		X		X			X
Photographs	Х	Х		Х		Х			Х		X		Х			Х		Х		Х			Х
Sensi-Care Product Application Arm		х	X	X	Х	Х	X	X	X	Х	Х	Х	Х	Х	Х	Х	X	X	X	X	X		x
Cavilon Application		Х		Х		Х			Х		Х		Х			Х		Х		Х			
Clean Trace Assessment				X		Х			X		X		Х			Х		X		X			
*Product Application – Timing & Product Use				X																			
Healthcare Worker Ease of Use Survey		Х																					X
Incontinence Episode Care/Tracking		Х	X	X	Х	X	Х	Х	X	X	X	X	Х	Х	Х	X	X	X	X	X	Х	Х	X
Adverse Events		Х	Х	Х	Х	Х	Х	Х	Х	Х	Х	Х	Х	Х	Х	Х	Х	X	Х	Х	Х	Х	Х

* Only required for first Subjects in each product group

12. Subject Discontinuation

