The Investigator may discontinue individual subjects from the study at any time. Subjects may voluntarily withdraw from the study at any time. The Investigator or study nurse will indicate on the appropriate CRF reason for, and date of, subject discontinuation.

Possible reasons for discontinuation are listed below:

- A subject develops a pressure ulcer in the sacral area (stage 3, 4, or unstageable, or any Deep Tissue Injury). The data from such a subject will be kept and analyzed to include the time during which the subject was in the study without a pressure ulcer.
- A subject develops a bacterial or fungal infection in the area included in the study or any other condition requiring the use of a topical treatment. Data collected up to the time where the subject required topical treatment will be analyzed.
- A subject develops any condition which, in the opinion of the Investigator, requires discontinuation from the study. If this condition is a suspected localized allergic reaction to the Cavilon Advanced Skin Protectant product, then appropriate testing confirmation should be performed and results/reports should be submitted to 3M. In addition, the event should be entered on the Adverse Event CRF.

The expectation is that subjects will be enrolled in this study for a period of 21 days. A subject who discontinues before the second IAD assessment, will be replaced with another qualified subject who will follow the same randomization scheme as the discontinued subject.

Subjects discontinued from the study will be returned to standard care and no further follow-up for this study will be performed.

13. Subject Compliance

Subject compliance is not an issue in this study as subjects will not be applying the product themselves. CRFs will be used to monitor the number of cleansing episodes, and number of product application(s), performed by skilled care givers.

14. Study Supplies

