19.1 Statistical Methods

19.1.1 Efficacy Analyses

The primary analysis will be the percent change from baseline to last visit in IAD scores. The IAD score at each time point will be estimated using the assessments at each time point. The percent change from baseline will be calculated at the last visit and compared between treatment groups using an analysis of variance with site, treatment, age group (infants vs adults) and interactions as factors in the model. Lack of significance (P<0.05) for the age group-by-treatment will be used as justification for pooling the age groups. If the interaction is significant, the age groups will be analyzed separately. If appropriate, non-parametric procedures (e.g. ranking the data prior to analysis) will be used.

The primary analysis will be done using an intent-to-treat (ITT) population, using all subjects who have at least one dose of their assigned product. For this analysis, dropouts will be considered censored at the time of dropping out. Because two primary endpoints are being tested, Hocherg's procedure will be used to determine statistical significance to preserve the Type I error rate of α =0.05.

A second analysis will be done using a per protocol (PP) set. This analysis will be done on those subjects who were compliant with therapy and completed all procedures. This dataset will be defined prior to database lock, and all reasons for exclusion will be documented.

Analytical methods will be defined in detail in the approved Statistical Analysis Plan (SAP).

Secondary efficacy endpoints in this study will include:

- Time to resolution of severe Category 2 IAD, defined as re-epithelialization of skin. The time to resolution will be tested using a Cox Proportional Hazards model, with treatment group as a fixed factor in the model, and center as a random factor in the model. Other important prognostic factors (e.g., age, type and intensity of incontinence, use of corticosteroids, diabetes, use of warfarin) will be identified and may be included as covariates in the model. Kaplan-Meier estimates of time to re-epithelialization will also be done.

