- Prevention of complications such as fungal infections and or pressure ulcer development will be summarized.
- Environmental cleanliness of multi-use comparative product packaging. The definition of a "clean" device will be one with a reading of <200. The proportion cleaned will be summarized.

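### No skin score is required when a subject is discontinued for an infection or pressure ulcer, so the last-visit primary analysis can use a score from before the event

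*Combined protocol and SAP*

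**What the plan says.** - **Section 12, data kept.** Among the reasons for discontinuation are a severe sacral pressure ulcer (stage 3, 4, unstageable or deep tissue injury) and an infection or other condition in the study area that needs topical treatment. In the ulcer case the data are kept and "analyzed to include the time during which the subject was in the study without a pressure ulcer". In the infection case, "Data collected up to the time where the subject required topical treatment will be analyzed".
- **Section 12, follow-up.** "Subjects discontinued from the study will be returned to standard care and no further follow-up for this study will be performed".
- **Section 11.2.** "The subject's participation in this study is completed after 21-42 -days of follow-up or when the subject is discharged from the facility". The final-visit list, which includes the skin assessment and photographs, follows from that sentence. Discontinuation is not mentioned.
- **Sections 6.4 and 11.1.** A paediatric subject crossing over from paste is to have a skin assessment and photographs before the switch. Section 12 has no counterpart for subjects who leave.
- **Section 19.1.1.** Percent change in IAD score is taken at the last visit and compared by analysis of variance. "The primary analysis will be done using an intent-to-treat (ITT) population", and dropouts are to be treated as censored.
- **Section 19.4.** Missing critical efficacy data are imputed by last observation carried forward; the examples given are time variables. A sensitivity analysis of the primary endpoint counts every dropout in both arms as worsening.

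**The concern.** Exits for infection or pressure ulcer are related to outcome. Avoiding these complications is a named secondary outcome, and the sponsor expects the products to differ on it, so unequal exit rates are plausible. If the skin has deteriorated by the day of exit and nobody scores it, the subject contributes the last routine score instead. The analysis labelled intent-to-treat then measures, for these subjects, skin condition up to the complication. Unequal exit rates would bias the treatment difference.

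The gap has to be closed at data collection. Section 19.1.1 leaves analytical detail to a SAP, but a SAP cannot supply a score that was never taken.

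**Working it through.** **1. How old the last score can be.** The Schedule of Events places skin scores on days 1, 3, 5, 8, 10, 12, 15, 17, 19 and End of Study. The gaps are 2 or 3 days, so without an exit score the last available score can be up to about 3 days old. Section 12 replaces subjects who leave before the second IAD assessment, and Section 19.4 excludes replaced subjects, so the issue concerns later exits. (Section 6.1 says first assessment where Section 12 says second; the two must be reconciled.)

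**2. The plan's own figure.** Section 19.2 gives SD 70, difference 45, 51 per arm, power at least 80%. With SE = 70 × √(2/51) = 13.86, 45/13.86 = 3.246 and 3.246 − 1.960 = 1.286, power is 90.1% (two-sided 0.05, normal approximation). The stated bound is met, and nothing below makes it wrong.

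**3. Bias in the treatment difference.** Let fT and fC be the proportions leaving for a complication (test, paste). Let g be the percentage-point gap between the last pre-event score and the score on the day of exit. Negative change is improvement. Then

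bias = recorded difference − difference with exit scores = −(fT − fC) × g.

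The documents give neither f nor g. Assumed ranges: f 5-20%, g 25-100. At 51 per arm, 5% is about 3 subjects and 20% about 10.

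| Exits, test vs paste | g = 25 | g = 50 | g = 100 |
|---|---|---|---|
| equal | 0 | 0 | 0 |
| 10% vs 5% | −1.25 | −2.5 | −5 |
| 20% vs 10% | −2.5 | −5 | −10 |
| 20% vs 5% | −3.75 | −7.5 | −15 |
| 5% vs 20% | +3.75 | +7.5 | +15 |

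The largest entry is 0.15 × 100 = 15 points, and 15/45 = 33% of the design difference. A negative entry flatters the test product; a positive one works against it.

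**4. Effect on inference.** Take a recorded difference of −45 and an arm variance with exit scores of 70² + f(1 − f)g².

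- 20% vs 5%, g = 100: the difference with exit scores is −30, the variances are 6,500 and 5,375, SE = √(11,875/51) = 15.26, and power is 50.2%. At g = 50 it is 75.1%.
- 10% vs 5%: 88.1%, 85.4% and 77.1% for g = 25, 50 and 100.
- 5% vs 20%, g = 50: the difference is −52.5 and power 95.8%.
- Equal rates: no bias, and power between 89.9% (5%, g = 25) and 80.5% (20%, g = 100).

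If the true difference with exit scores is zero, two-sided rejection under the present rule is 5.4% (10% vs 5%, g = 50), 8.4% (20% vs 5%, g = 50) or 19.1% (20% vs 5%, g = 100).

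**5. How large g could be.** Appendix A scores epidermal loss (30 per area band) and colour of intact skin (1 per band). It has no item for infection, although the severity table in Section 10 lists skin infection as a Category 2 sign. An infection that changes neither feature gives g = 0. One further band of epidermal loss in one zone adds 30, ignoring colour and assuming zone scores are summed. That is 30/120 = 25, 30/60 = 50 or 30/30 = 100 percentage points for a baseline total of 120, 60 or 30, and less for a higher baseline. The assumed range is possible, but the documents do not establish it.

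**6. What the analysis section does with these subjects.** Section 19.1.1 uses the last visit and also calls dropouts censored, which has no meaning for an analysis of variance of percent change. Section 19.4 uses last observation carried forward. No single rule results. The worsening analysis has no numerical value, so it cannot be run as written.

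**The case against.** The strongest reply is that the text is loose rather than wrong, and much of that stands.

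- A reader might infer that data are cut before the infection. The infection sentence runs to the need for topical treatment, so a same-day score is not excluded. Only the ulcer sentence is limited to event-free time.
- A reader might infer that failures are analysed on their last good score. It is the last available score and may already be poor. Section 11.1 has staff look for infections and ulcers at the scoring visits, so some complications will be found on a scored day.
- A reader might infer that exit scoring is ruled out. Section 7.1 runs the endpoint to the end of participation, and the Schedule of Events and the CRF table in Section 16.3 have an End of Study skin score. These could cover early exits, so exit scoring is unspecified, not forbidden.
- A reader might infer that the complications go uncounted. Section 12 records reason and date of discontinuation, Section 7.3 summarises discontinuations by reason, and Section 19.1.1 states: "Prevention of complications such as fungal infections and or pressure ulcer development will be summarized". Nothing says to drop the terminating event.
- The listed reasons are not mandatory: "Possible reasons for discontinuation are listed below".
- Section 2 stresses telling IAD from pressure ulcers, which is a fair motive for the ulcer-free cut. It supports saying how ulcerated skin is scored; it does not support leaving the exit unscored.
- If paste has more complications, as the sponsor expects, the bias works against the test product.

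What remains is that no sentence requires the exit score, two sentences restrict what is analysed, and the primary handling is not uniquely defined.

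**Conclusion.** The point holds as a gap in data collection and in the primary-analysis rule. A subject discontinued for a complication can be analysed on a pre-event score up to about 3 days old, and only an incompletely specified sensitivity analysis responds to this.

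The size is not known. Under assumed exits of 5-20% per arm and gaps of 25-100 points, the bias in the difference runs from 0 with equal rates to 15 points at 20% against 5% with a 100-point gap. It may be near zero if infection leaves epidermal loss and colour unchanged.

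A reader might infer that the plan is tilted towards the test product. The documents do not support that, because the direction depends on which arm has more such exits.

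**What to change.** 1. In Sections 11.2 and 12, state that the existing End of Study skin score and photographs are done on the day of any discontinuation, where the subject agrees and without delaying care.
2. Amend the two data-cut sentences in Section 12 so that this exit score is the subject's last-visit score in the ITT primary analysis, and say how ulcerated skin is scored.
3. In Section 19.1.1, replace 'censored' with that single rule. In Section 19.4, give the value used for 'worsening'.
4. Confirm that an infection or pressure ulcer leading to discontinuation counts in the complications summary. The exit score alone will not register an infection that leaves epidermal loss and skin colour unchanged.

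The cost is protocol wording and one more use of an existing form per discontinued subject. Some exit scores will be less favourable than those used now. No stopping or treatment rule changes.

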All nine patients who reported pain at the beginning of the study reported reduction from scores of 7 to 10 to scores of 0 to 3 at study end. The barrier film was therefore able to provide substantial pain reduction in all patients who reported pain at enrollment, with reduction of patient scores from 7-10 at Day 1 to 0-3 at study end. The protective nature of the barrier film with skin healing reduced reported pain scores during cleansing and subsequent product applications.

There were no reported adverse events associated with the barrier film application. The formulation was able to polymerize and able to create a protective barrier in the presence of oozing exudates and blood.

This product has also been tested in hairless guinea pig and Yorkshire pig models. These studies have demonstrated the formulation's ability to protect Dermatome created superficial wounds from an artificial intestinal fluid for up to 96 hours, and allow healing under continued exposure to the artificial intestinal fluid. In porcine partial thickness wounds, the formulations were able to polymerize and

create a barrier in the presence of exudate and blood, demonstrating hemostatic and lymphostatic properties.

Ten (10) human clinical studies have been completed on healthy subjects, with the product being applied to the back, arms, and buttocks. No adverse events were reported, and no irritation or sensitization was observed in single or multiple dose (N=5 doses on buttocks) in studies involving healthy subjects. The product was well tolerated. A product durability study was completed with the final dosing recommendation of twice a week to three times a week dosing depending on whether there is intact or partial denuded skin.

5. Study Objectives and Purpose

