17.4 Risk to Benefit Rationale

The study product is investigational and is classified as non-significant risk. Based on data collected in previous studies, the risk-to-benefit ratio is within reason for foreseeable risks. However, appropriate observation and follow-up of subjects, will still be required as outlined in the protocol.

18. Safety Reporting

Adverse events will be collected for subjects beginning at Day 1 through the final study visit, or until the subject is discharged from the facility. An adverse event is any symptom, sign, illness, or experience, which develops or worsens during the course of the study, which may or may not be considered investigational product related. The principal measures of safety will be the incidence of adverse events reported during the study.

An anticipated adverse event in this study is a skin reaction to the investigative product itself. Worsening of IAD is expected in this subject population and would therefore not constitute an adverse event (related to the product being tested).

The Adverse Event CRF will be used to capture any safety-related concerns.

18.1Adverse Events

The Investigator is responsible for identifying and reporting adverse events experienced by each subject throughout the study. An adverse event can occur at any time during the conduct of the study, in any phase of the study, or after the study is completed. An adverse event can be identified by the Investigator or reported by the subject.

Note: The Federal Privacy Rule (HIPAA) specifically permits the use and disclosure of protected health information "without written authorization of the individual" when used for public health activities such as reporting adverse events, tracking FDA-related products, enabling recalls, repairs, replacements, lookbacks, or conducting post-market surveillance [45 CFR 164.512]. This use and disclosure is subject to the *minimum necessary* standard, i.e. "the minimum necessary to accomplish the intended use, disclosure, or request" [45 CFR 164.502(b)(1)].

An adverse event is considered to be serious if it is:

- Life threatening of results in death
- Causes in-patient hospitalization
- Unduly prolongs hospitalization
- Persistently or significantly disabling
- A congenital anomaly
- Requires intervention to prevent outcomes above

Severity:

All adverse events will be classified as one of the following severities:

Mild: Subject is aware of signs or symptoms but they are easily tolerated.

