18.2 Adverse Event Recording and Reporting

All adverse events will be recorded on the Adverse Event CRF. The Investigator will record each product-related adverse event on an Adverse Device Effect Record. Event documentation will include the description, severity, seriousness, date of onset and resolution, relationship to the investigational product, action taken, and outcome.

Relatedness:

Definitely related:	Follows a reasonable temporal sequence from investigational product application, and cannot be reasonably explained by known characteristics of the patient's clinical data.
Possibly related:	Follows a reasonable temporal sequence from investigational product application but could have been produced by the patient's clinical state regardless of the investigational product.
Probably not related:	Temporal association is such that the investigational product is not likely to have had any reasonable association with the observed event.
Not related:	No relationship to investigational product is perceived

Not related: No relationship to investigational product is perceived.

The Investigator must promptly report an adverse device effect to the site monitor. If the adverse device effect is also considered by the Investigator to be serious and/or unanticipated, the Investigator must report it to the IRB as soon as possible and within IRB requirements.

A serious adverse event (SAE) involving a non-3M commercialized product is to be reported to the site monitor and the IRB.

If a subject has no adverse device effect during the study, the absence of such must be recorded on the CRF.

19. Statistics

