1. DANGER! EXTREMELY FLAMMABLE!

- 2. Cavilon Advanced Skin Protectant is extremely flammable until it has completely dried on the skin.
- 3. Cavilon Advanced Skin Protectant should only be applied when no ignition sources or heat-producing devices are in use.
- 4. Avoid using Cavilon Advanced Skin Protectant around flames.
- 5. Use Cavilon Advanced Skin Protectant only in well ventilated area.
- 6. Avoid use on individuals who are allergic to any of the ingredients.
- 7. The product is individually packaged for single use only. Reuse could result in increased risk of infection, or inadequate product performance.
- 8. Cavilon Advanced Skin Protectant is not intended for applications requiring sterile product (e.g. infusion catheter site protection and care or surgical site protection).
- 9. Keep out of the reach of children.

Precautions

- 1. Skin absorption and the effectiveness of topical medications (including: antimicrobials, antifungals, and analgesics) may be reduced or prevented by the presence of the Cavilon Advanced Skin Protectant.
- 2. Use of other barrier products, ointments, creams or lotions may significantly reduce the effectiveness of the product.
- 3. The product can increase the adhesion of some adhesive products.

Directions for Use

- Cleanse skin before applying Cavilon Advanced Skin Protectant. Gently dry areas of intact skin. If areas of erosion (denudement) are present, excess serous or serosanguinous drainage may be blotted with a gauze pad if necessary.
- Grasp applicator and place thumb at the end of the lever. Aim the sponge end of the applicator downward and firmly depress the lever to break the internal ampule. (Figure 1) A snapping or popping noise will be noted as the ampule breaks.

Page 51 of 54 Status: Release Version: 7 Issue Date: 8/31/2016 12:19:02 PM

Figure 1

- Keep the applicator pointed in a downward position for approximately 10 seconds. Fluid will flow into the foam sponge; continued pressure on the lever is not required. Fluid will not completely saturate the sponge to the edges.
- 4) Using an even, sweeping motion, gently wipe the foam sponge across the skin (Figure 2); downward pressure on the applicator is not needed and may result in pooling of fluid. Move to adjacent unprotected area and repeat application until the entire area of concern has been covered.

Figure 3

If an area is missed, wait until the fluid has dried completely before applying additional product.

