- 5) If Cavilon Advanced Skin Protectant is applied within a skin fold or other area of skin-to-skin contact, make sure that the skin surfaces are separated to allow the fluid to dry completely (30 seconds) before allowing skin to return to the normal position.
- 6) When used under adhesive tapes, dressings, or devices allow Cavilon Advanced Skin Protectant to dry for approximately 1 minute before covering with adhesive products. Refer to Precaution Statement # 3.
- 7) Cleanse affected area as needed. Cavilon Advanced Skin Protectant is waterproof and is not removed by cleansing.

8) Removal is not required. If desired, the film can be removed with an adhesive remover containing hexamethyldisiloxane (HMDS).

9) Reapply two to three times per week. More frequent application may result in buildup of the product.

Storage/ Shelf Life/Disposal

For best results, the product should be stored in a cool and dry environment. Avoid excessive heat.

For shelf life, refer to the expiration date on each package.

Refer to facility policy for disposal.

How supplied

Applicators are individually packaged for single patient one time use only. The solution is non-sterile. The applicator is sterile if package is intact. Do not use if the package is damaged or opened.

32. APPENDIX C – Instructions for Use of 3M[™] Cavilon[™] No Rinse Skin Cleanser #3380

- Moisten a clean cloth with 3M[™] Cavilon[™] No-Rinse Skin Cleanser or water.
- Spray affected area with 3M[™] Cavilon[™] No-Rinse Skin Cleanser.
- Gently wipe skin with the clean cloth to remove urine, stool or soil. Rinsing is not needed.
- Repeat as needed.

33. APPENDIX D – Manufacturer's instructions for ConvaTec Sensi-Care® Protective Barrier (part number 325614)

Active ingredients: Petrolatum 49%, skin protectant; Zinc oxide 15%, skin protectant

Directions: For skin protection: Apply as needed. For diaper rash: Change wet and soiled diapers promptly, cleanse the diaper area, and allow to dry. Apply liberally, as often as necessary, with each diaper change, especially at bedtime or any time when exposure to wet diapers may be prolonged.

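### Follow-up stops at discontinuation or discharge, so adverse events still ongoing at exit cannot be given the resolution date, outcome and final seriousness that the protocol asks for

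*Combined protocol and SAP*

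**What the plan says.** Four parts of the protocol bear on this.

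- **Section 12, Subject Discontinuation.** The possible reasons for discontinuation include a serious sacral pressure ulcer, a bacterial or fungal infection in the study area, any other condition needing topical treatment, and any condition that the investigator judges to require it, with suspected local allergy to Cavilon named. The section closes with: "Subjects discontinued from the study will be returned to standard care and no further follow-up for this study will be performed". No reason for leaving is exempted. For suspected allergy only, the section asks for confirmatory testing, a report to the sponsor and an AE form entry.
- **Section 18, opening paragraph.** "Adverse events will be collected for subjects beginning at Day 1 through the final study visit, or until the subject is discharged from the facility".
- **Section 18.2.** The documentation of an event covers its description, "severity, seriousness, date of onset and resolution, relationship to the investigational product, action taken, and outcome".
- **Section 22.** The investigator must document, report and evaluate each AE, and supply the sponsor with further safety information on particular events.

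Section 18.1 adds that an AE can arise "in any phase of the study, or after the study is completed". Section 11.2 lists an AE review, skin assessment and photographs at the final visit. It ties that visit to the end of the follow-up period or to discharge, and does not say whether a subject discontinued early receives it.

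**The concern.** Several of the events that end a subject's participation are the ones the trial most needs to describe. Safety is part of the primary objective (section 5.1). A skin reaction to the product is the anticipated AE (section 18). Fungal infection and pressure ulcer are complications listed among the secondary endpoints (section 7.2). Under section 12, study follow-up ends when such an event leads to discontinuation.

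Two things are at stake. The first is the record of how these events ended and how long they lasted. The second is seriousness. Two of the criteria in section 18.1, undue prolongation of a hospital stay and persistent or significant disability, depend on what happens after onset. Under section 18.2, an adverse device effect that the investigator considers serious must go to the IRB. A classification frozen at exit can therefore also affect reporting.

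**Working it through.** The protocol states no figure on this point, so the check is a cross-reading followed by a short day count.

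**Step 1. Sort events by when they resolve.**

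| Event | Section 12 (follow-up) | Section 18 (AE window) | Section 18.2 (resolution date, outcome) | Can all be met? |
|---|---|---|---|---|
| Starts and resolves before exit | Not engaged | Inside window | Can be completed | Yes |
| Ongoing at discontinuation | Follow-up ended | No rule for open events | Resolution date and final outcome not obtainable from study follow-up | No |
| Ongoing at discharge | Participation complete (sections 6.4, 11.2) | Window closed | As above | No |
| Starts after exit | Follow-up ended | Outside window | Not engaged | Yes; simply not collected |

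The conflict lies in the two middle rows. The last row is not a contradiction: the section 18.1 remark says when an AE can happen, while the opening of section 18 sets when AEs are collected.

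**Step 2. The allergy exception.** For a suspected local allergic reaction, section 12 itself asks for testing and a report to the sponsor. Some information therefore arrives after the decision to discontinue. It concerns the cause. Clinical resolution is still not followed.

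**Step 3. Seriousness.** Take an infection that leads to discontinuation and looks non-serious that day. If it later prolongs the stay unduly, it meets a section 18.1 criterion, but section 12 has ended the follow-up that would show this.

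**Step 4. Is early exit foreseen?** Yes. Inclusion criterion 6 asks only for an expected stay of at least 7 days, against a 21-day treatment period (21 − 7 = 14 days not covered by that expectation). Discharge before day 21 still counts as completion. With 102 subjects planned and no AE or discontinuation rate in the documents, the number leaving with an open event cannot be calculated.

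**Step 5. Observation after the last Cavilon application in scheduled completers.** End of Study is D22. There are nine applications in the Schedule of Events, and section 10 sets the week 1 pattern, with M-W-F afterwards.

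- Monday start (as in the Schedule): application 9 on D19; 22 − 19 = 3 days.
- Tuesday start: D1, 3, 5, 7, 9, 11, 14, 16, 18; 22 − 18 = 4 days.
- Wednesday start: D1, 3, 6, 8, 10, 13, 15, 17, 20; 22 − 20 = 2 days.
- Thursday start: D1, 3, 5, 7, 9, 12, 14, 16, 19; 22 − 19 = 3 days.

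Subjects who complete the schedule are thus seen 2 to 4 days after the last application. A subject who exits on an application day can have 0 days, and the share of such subjects is unknown.

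**The case against.** The strongest reply is that little is lost. The event that causes discontinuation is itself recorded. The planned safety analysis is incidence by nature, relation and severity (sections 7.3 and 19.1.2), and no analysis of AE duration or outcome is planned. A site could enter an open event as ongoing. Section 22 gives the investigator a general duty on every AE. The AE form instructions cited in sections 11.1 and 11.2 are not among the documents and may already cover open events.

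Much of this stands. The incidence comparison is largely unaffected. But the protocol nowhere says that an open event may be coded as ongoing, and such a code supplies neither a resolution date nor a final seriousness. The general duty in section 22 also sits against an explicit sentence in section 12, so a site has to choose between them.

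A reader might go further and infer four things that the documents do not support.

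- *Outcomes are lost for everyone who discontinues.* Only events open at exit are affected.
- *Film left on the skin goes unobserved beyond its known duration.* The figure behind this is the ability "to protect Dermatome created superficial wounds from an artificial intestinal fluid for up to 96 hours", which comes from animal models. It measures neither wear time on incontinent human skin nor the delay before a skin reaction. Scheduled completers are also observed for 2 to 4 days after the last application.
- *The loss falls on the Cavilon arm.* The film "is waterproof and is not removed by cleansing" (Appendix B), but section 6.2 says that the paste can also leave residue after cleansing. No passage shows a difference between arms in AE loss.
- *The passages on film and topical treatment contradict each other.* Appendix B warns of reduced topical effect, and section 11.1 and Appendix B describe removal where needed or wanted. A warning together with an as-needed method is coherent.

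**Conclusion.** The concern holds for AEs still ongoing at discontinuation or discharge, including infections, serious pressure ulcers and skin reactions that themselves caused the exit. For these, sections 12, 18, 18.2 and 22 cannot all be satisfied, apart from the partial allergy exception, and an event that later meets a seriousness criterion may stay classified as non-serious.

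The size in subjects is unknown. The consequence is incomplete safety description and possibly missed serious classifications. It does not bias the efficacy analysis, and the AE incidence comparison remains usable. The conclusion assumes that the AE form instructions do not already contain a rule for open events; if they do, the protocol text still needs to be aligned with them. This is a worthwhile and inexpensive correction to the safety record.

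**What to change.** Reconcile sections 12, 18 and 18.2 by amendment:

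1. In section 12, limit the sentence ending follow-up to efficacy assessments.
2. In section 18, state that in both arms any AE ongoing at discontinuation or discharge, and any event that caused discontinuation, is followed from the facility record or by one call until it is resolved or stable.
3. In section 18.2, state that the resolution date, the outcome (with ongoing as a permitted entry) and the final seriousness are entered on the existing AE form.
4. In section 11.2, state whether subjects discontinued early receive the final-visit assessments.

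This is a rule for collecting data and changes nothing in treatment. The cost is amendment wording, some site time for record checks or calls, and an occasional subject who cannot be reached after discharge. No new form is needed, and randomization and the efficacy analyses are untouched.
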